10.4.2.3 Exploratory Endpoint Analyses

The percent change and change from baseline in laboratory based exploratory endpoints at each scheduled visit will be summarized. For achieving LDL-C < 70 mg/dL, subjects missing LDL-C for a particular planned visit will be considered as not achieving LDL-C < 70 mg/dL. For continuous exploratory endpoints, the same model as for the secondary endpoint analyses may be used for estimating treatment group means and differences at weeks 48 and 104.

Subgroup analyses for exploratory endpoints may be conducted on baseline covariates specified in Section 10.1.6.

10.4.2.4 Safety Endpoint Analyses

Safety Laboratory Parameters

Laboratory parameters will be summarized for each treatment group using descriptive statistics at each scheduled visit. Laboratory shift tables for certain analytes will be provided using the CTCAE v.4 toxicity criteria. The results will be based on the maximum (ie, worst) shift from baseline to the end of study.

Vital Signs

Vital signs will be summarized for each treatment group using descriptive statistics at each scheduled visit.

Anti-AMG 145 antibodies

The incidence and percentages of subjects who develop anti-AMG 145 antibodies (binding and neutralizing) at anytime will be tabulated.

Concomitant Medications

Concomitant medications of interest will be summarized for each treatment group.

11. REGULATORY OBLIGATIONS

11.1 Informed Consent

An initial generic informed consent template form is provided for the investigator to use to customize accordingly to his or her site's requirements. Updates to the template will be communicated by letter from the Amgen study manager to the investigator. The written informed consent document should be prepared in the language(s) of the potential subject population.

Before a subject's participation in the clinical study, the investigator is responsible for obtaining written informed consent from the subject after adequate explanation of the aims, methods, anticipated benefits, and potential hazards of the study and before any protocol-specific screening procedures or any investigational products are administered.

The acquisition of informed consent should be documented in the subject's medical records, and the informed consent form should be signed and personally dated by the subject and by the person who conducted the informed consent discussion. The original signed informed consent form should be retained in accordance with institutional policy, and a copy of the signed consent form should be provided to the subject.

If a potential subject is illiterate or visually impaired and does not have a legally acceptable representative, the investigator must provide an impartial witness to read the informed consent form to the subject and must allow for questions. Thereafter, both the subject and the witness must sign the informed consent form to attest that informed consent was freely given and understood.

11.2 Independent Ethics Committee/Institutional Review Board (IEC/IRB)

A copy of the protocol, proposed informed consent form, other written subject information, and any proposed advertising material must be submitted to the IEC/IRB for written approval. A copy of the written approval of the protocol and informed consent form must be received by Amgen before recruitment of subjects into the study and shipment of Amgen investigational product.

The investigator must submit and, where necessary, obtain approval from the IEC/IRB for all subsequent protocol amendments and changes to the informed consent document. The investigator should notify the IEC/IRB of deviations from the protocol or

serious adverse events occurring at the site and other adverse event reports received from Amgen, in accordance with local procedures.

The investigator will be responsible for obtaining annual IEC/IRB approval/renewal throughout the duration of the study. Copies of the investigator's reports and the IEC/IRB continuance of approval must be sent to Amgen.

11.3 Subject Confidentiality

The investigator must ensure that the subject's confidentiality is maintained:

- On the CRFs or other documents submitted to Amgen, subjects should be identified by a subject identification number on the demographics CRF.
- For Serious Adverse Events reported to Amgen, subjects should be identified by a subject identification number.
- Documents that are not for submission to Amgen (eg, signed informed consent forms) should be kept in strict confidence by the investigator.

In compliance with Federal regulations/ International Conference on Harmonization (ICH) GCP Guidelines, it is required that the investigator and institution permit authorized representatives of the company, of the regulatory agency(s), and the IEC/IRB direct access to review the subject's original medical records for verification of study-related procedures and data. Direct access includes examining, analyzing, verifying, and reproducing any records and reports that are important to the evaluation of the study. The investigator is obligated to inform and obtain the consent of the subject to permit named representatives to have access to his/her study-related records, including personal information, without violating the confidentiality of the subject.

11.4 Investigator Signatory Obligations

Each clinical study report should be signed by the investigator or, in the case of multicenter studies, the coordinating investigator.

The coordinating investigator, identified by Amgen, will either be:

- a recognized expert in the therapeutic area
- an investigator who provided significant contributions to either the design or interpretation of the study
- an investigator contributing a high number of eligible subjects

12. ADMINISTRATIVE AND LEGAL OBLIGATIONS

12.1 Protocol Amendments and Study Termination

If Amgen amends the protocol, agreement from the investigator must be obtained. The IEC/IRB must be informed of all amendments and give approval. The investigator must send a copy of the approval letter from the IEC/IRB to Amgen.

Amgen reserves the right to terminate the study at any time. Both Amgen and the investigator reserve the right to terminate the investigator's participation in the study according to the study contract. The investigator should notify the IEC/IRB in writing of the study's completion or early termination and send a copy of the notification to Amgen.

Subjects may be eligible for continued treatment with Amgen investigational product (IP) by an extension protocol or as provided for by the local country's regulatory mechanism. However, Amgen reserves the unilateral right, at its sole discretion, to determine whether to supply Amgen (IP), and by what mechanism, after termination of the trial and before it is available commercially.

12.2 Study Documentation and Archive

The investigator should maintain a list of appropriately qualified persons to whom he/she has delegated study responsibilities. All persons authorized to make entries and/or corrections on CRFs will be included on the Amgen Delegation of Authority Form.

Source documents are original documents, data, and records from which the subject's CRF data are obtained. These include but are not limited to hospital records, clinical and office charts, laboratory and pharmacy records, diaries, microfiches, radiographs, and correspondence.

The investigator and study staff are responsible for maintaining a comprehensive and centralized filing system of all study-related (essential) documentation, suitable for inspection at any time by representatives from Amgen and/or applicable regulatory authorities.

Elements should include:

- Subject files containing completed study-related worksheets, informed consent forms, and subject identification list
- Study files containing the protocol with all amendments, investigator's brochure, copies of pre-study documentation, and all correspondence to and from the IEC/IRB and Amgen
- If kept, proof of receipt/delivery sheet, Investigational Product Accountability Record, Return of Investigational Product for Destruction, Final Investigational Product Reconciliation Statement (if applicable), and all drug-related correspondence

In addition, all original source documents supporting entries in the CRFs must be maintained and be readily available.

Retention of study documents will be governed by the Clinical Trial Agreement.

12.3 Study Monitoring and Data Collection

The Amgen representative and regulatory authority inspectors are responsible for contacting and visiting the investigator for the purpose of inspecting the facilities and, upon request, inspecting the various records of the clinical study (eg, CRFs and other pertinent data) provided that subject confidentiality is respected.

The Amgen monitor is responsible for verifying the CRFs at regular intervals throughout the study to verify adherence to the protocol; completeness, accuracy, and consistency of the data; and adherence to local regulations on the conduct of clinical research. The monitor should have access to subject medical records and other study-related records needed to verify the entries on the CRFs.

The investigator agrees to cooperate with the monitor to ensure that any problems detected in the course of these monitoring visits, including delays in completing CRFs, are resolved.

In accordance with ICH GCP and the sponsor's audit plans, this study may be selected for audit by representatives from Amgen's Global Compliance Auditing function (or designees). Inspection of site facilities (eg, pharmacy, drug storage areas, laboratories) and review of study-related records will occur to evaluate the study conduct and compliance with the protocol, ICH GCP, and applicable regulatory requirements.

Data capture for this study is planned to be electronic:

- All source documentation supporting entries into the electronic CRFs must be maintained and readily available.
- Updates to electronic CRFs (eCRF) will be automatically documented through the software's "audit trail".
- To ensure the quality of clinical data across all subjects and sites, a clinical data management review will be performed on subject data received at Amgen. During this review, subject data will be checked for consistency, omissions, and any apparent discrepancies. In addition, the data will be reviewed for adherence to the protocol and GCP. To resolve any questions arising from the clinical data management review process, data queries and/or site notifications will be created in the EDC system database for site resolution and closed by Amgen reviewer.
- The principal investigator signs only the Investigator Verification Form for this electronic data capture study. This signature will indicate that the principal investigator inspected or reviewed the data on the CRF, the data queries, and the site notifications, and agrees with the content.

Amgen (or designee) will perform self-evident corrections to obvious data errors in the clinical trial database, as documented in the Study Specific Self Evident Corrections Plan. Examples of obvious data errors that may be corrected by Amgen (or designee)

include deletion of obvious duplicate data (eg, same results sent twice with the same date with different visit—Week 4 and early termination) and clarifying “other, specify” if data are provided (eg, race, physical examination). Each investigative site will be provided a list of the types of corrections applied to study data at the initiation of the trial and at study closeout.

12.4 Investigator Responsibilities for Data Collection

The Investigator is responsible to comply with the requirements for all assessments and data collection (including subjects not receiving protocol-required therapies) as stipulated in the protocol for each subject in the study. For subjects who withdraw prior to completion of all protocol-required visits and are unable or unwilling to continue the Schedule of Assessments ([Appendix A](#)), the Investigator can search publically available records [where permitted] to ascertain survival status. This ensures that the data set(s) produced as an outcome of the study is/are as comprehensive as possible.

12.5 Language

eCRFs must be completed in English. TRADENAMES[®] (if used) for concomitant medications may be entered in the local language.

All written information and other material to be used by subjects and investigative staff must use vocabulary and language that are clearly understood. Consult the country-specific requirements for language requirements.

12.6 Publication Policy

To coordinate dissemination of data from this study, Amgen encourages the formation of a publication committee consisting of several principal investigators and appropriate Amgen staff, the governance and responsibilities of which are set forth in a Publication Charter. The committee is expected to solicit input and assistance from other investigators and to collaborate with authors and Amgen staff as appropriate as defined in the Publication Charter. Membership on the committee (both for investigators and Amgen staff) does not guarantee authorship—the criteria described below should be met for every publication.

Authorship of any publications resulting from this study will be determined on the basis of the Uniform Requirement for Manuscripts Submitted to Biomedical Journals (International Committee of Medical Journal Editors), which states:

- Authorship credit should be based on (1) substantial contributions to conception and design, acquisition of data, or analysis and interpretation of data; (2) drafting the

article or revising it critically for important intellectual content; (3) final approval of the version to be published. Authors should meet conditions 1, 2, and 3.

- When a large, multicenter group has conducted the work, the group should identify the individuals who accept direct responsibility for the manuscript. These individuals should fully meet the criteria for authorship defined above.
- Acquisition of funding, collection of data, or general supervision of the research group, alone, does not justify authorship.
- All persons designated as authors should qualify for authorship, and all those who qualify should be listed.
- Each author should have participated sufficiently in the work to take public responsibility for appropriate portions of the content.

All publications (eg, manuscripts, abstracts, oral/slide presentations, book chapters) based on this study must be submitted to Amgen for corporate review. The Clinical Study Agreement among the institution, principal investigator, and Amgen will detail the procedures for, and timing of, Amgen's review of publications.

12.7 Compensation

Any arrangements for compensation to subjects for injury or illness that arises in the study are described in the Compensation for Injury section of the Informed Consent. Depending on the type of study, and if permitted under applicable regional laws or regulatory guidelines, subjects may be compensated for other inconveniences not associated with study-related injuries (eg, travel costs).

14. APPENDICES

Appendix A. Schedule of Assessments

Applies to both AMG 145 and SOC-alone groups unless specified otherwise																				
Timepoint/Frequency	D1 ^a	W2 ^b	W4 ^{b/c}	W8 ^c	W12	W24	W36	W44 ^f	W46 ^g	W48	W50 ⁱ	W52 ^{i/j}	W56 ^j	W60	W72	W84	W96	W100 ^f	W102 ^g	W104
General Procedures																				
Informed consent	X																			
Medical history	X																			
Vital Signs (sitting BP, HR)	X	X	X	X	X	X	X	X	X	X	X	X	X	X	X	X	X	X	X	X
Review for AEs/SAEs	X	X ^e	X ^e	X ^e	X	X	X	X ^e	X ^e	X	X	X	X	X	X	X	X	X	X	X
Concomitant therapy	X	X ^e	X ^e	X ^e	X	X	X	X ^e	X ^e	X	X	X	X	X	X	X	X	X	X	X
Physical exam	X ^d																			X
Body weight	X									X										X
Randomization	X																			
Central Laboratory																				
Fasting lipids	X ^d				X	X				X				X ^k		X				X
ApoA1, ApoB, Lp(a)	X ^d				X	X				X				X ^k		X				X
Vitamin E ^h					X	X				X				X ^k		X				X
hsCRP	X ^d									X										X

Footnotes defined on last page of this table

Appendix A. Schedule of Assessments

Applies to both AMG 145 and SOC-alone groups unless specified otherwise																				
Timepoint/Frequency	D1 ^a	W2 ^b	W4 ^{b/c}	W8 ^c	W12	W24	W36	W44 ^f	W46 ^g	W48	W50 ⁱ	W52 ^{ij}	W56 ^j	W60	W72	W84	W96	W100 ^f	W102 ^g	W104
Central Laboratory																				
Chemistry, fasting glucose	X ^d				X	X				X				X ^k		X				X
Coagulation (PT/INR)	X									X										X
Hematology	X ^d				X	X				X				X ^k		X				X
TSH	X ^d																			
HbA1c	X ^d				X	X				X										X
Anti-AMG 145 antibodies	X ^d				X	X				X						X				X
HCV antibodies ^l	X ^d																			
HCV viral load ^l	X ^d				X	X				X				X ^k		X				X
Urine pregnancy, FSH ^m	X ^d				X	X				X				X ^k		X				X
Urinalysis	X ^d				X	X				X				X ^k		X				X
Urine microalbumin	X ^d				X	X				X				X ^k		X				X
Investigational Product																				
Subject without previous in home use experience: IP in-office administration	X ^{f/g}	X ^b	X ^{b/c}	X ^c				X	X	X ^{ij}	X ⁱ	X ^{ij}	X ^j					X	X	
Subject with previous in-home use experience: IP in-office administration	X ^{f/g}							X	X	X ^{ij}								X	X	
IP dispense	X		X ^b		X	X	X			X		X ⁱ		X	X	X	X			X
IP reconciliation					X	X	X	X	X					X	X	X	X	X	X	

Footnotes defined on last page of this table

Appendix A. Schedule of Assessments

Applies to both AMG 145 and SOC-alone groups unless specified otherwise					
Timepoint/Frequency	W116	W128	W140	W152	EOS Phone visit W156
General Procedures					
Vital Signs (sitting BP, HR)	X	X	X	X	
Review for AEs/SAEs	X	X	X	X	X
Concomitant therapy	X	X	X	X	X
Physical Exam				X	
Body Weight				X	
Laboratory					
Fasting lipids				X	
Chemistry, fasting glucose				X	
Hematology				X	
Coagulation (PT/INR)				X	
HbA1c				X	
Anti-AMG 145 antibodies				X	
HCV viral load ^l				X	
Urine pregnancy				X	
Investigational Product					
IP Dispense	X	X	X		
IP Reconcile	X	X	X	X	

Page 3 of 3

^a D1 = day of first administration of IP. This visit should also coincide with EOS visit for parent study; for visit windows see [Section 7](#) of the protocol. Procedures NOT conducted as part of EOS visit for parent study should be completed at this visit.

^b Training visit applies to subjects who are randomized to AMG 145 and select the Q2W regimen

^c Training visit applies to subjects who are randomized to AMG 145 and select QM regimen

^d Only if enrollment into 138 exceeds last laboratory visit from parent study by 30 days. Cardiac History Form will also need to be completed.

^e Telephone visit for subjects randomized to SOC-alone

^f Only for subjects receiving AMG 145 who have selected the QM regimen

^g Only for subjects receiving AMG 145 who have selected the Q2W regimen

^h Vitamin E samples will be drawn for all applicable visits, testing will be conducted by reflex when LDL-C is < 25 mg/dL

ⁱ Training visit applies to subjects who are randomized SOC-alone in year 1 and select the Q2W regimen in year 2

^j Training visit applies to subjects who are randomized SOC-alone in year 1 and select the QM regimen in year 2

^k Only for subjects randomized to placebo or SOC in parent study AND randomized to SOC-alone in Year 1

^l HCV antibodies only in high risk subjects (see [Section 7.1.2.4](#)) or if ALT or AST > 2x ULN; viral load only in subjects positive for HCV

^m FSH in applicable subjects for study entry only – see [exclusion criteria](#); urine pregnancy in females of childbearing potential

ⁿ Dispense IP for at-home injections (only for subjects who have previous experience of self-injecting AMG 145)

Appendix B. Additional Safety Assessment Information

Adverse Event Toxicity Grading Scale

Refer to the NCI Common Terminology Criteria for AEs (CTCAE) Version 4.0 for AE grading and information. The CTCAE is available at the following link:

http://ctep.cancer.gov/protocolDevelopment/electronic_applications/ctc.htm.

Drug-induced Liver Injury Reporting & Additional Assessments

Reporting

To facilitate appropriate monitoring for signals of DILI, cases of concurrent AST/ALT and TBL elevation according to the criteria specified in [Section 6.1.3.2](#) (3x ULN for AST/ALT and 2x ULN for TBL or INR>1.5 ULN) require the following:

- The event should be reported to Amgen as a serious adverse event within 24 hours of discovery or notification of the event (ie, before additional etiologic investigations have been concluded)
- The appropriate eCRF (eg, adverse event eCRF) that captures information necessary to facilitate the evaluation of treatment-emergent liver abnormalities should be completed.

Other events of hepatotoxicity and potential DILI should be reported as serious adverse events if they meet the criteria for a serious adverse event defined in [Section 9.2.1](#).

Additional Clinical Assessments and Observation

All subjects in whom IP is withheld due to potential DILI or who experience AST/ALT elevations >3x ULN should undergo a period of “close observation” until abnormalities return to normal or to the subject’s baseline levels. Assessments that should be performed during this period include:

- Repeat liver chemistries within 24-48 hours (ALT, AST, ALP, TBL); in cases of TBL >2x ULN or AST/ALT much greater than 3x ULN, retesting should be performed within 24 hours
 - Subjects should be monitored at least twice weekly; testing frequency may decrease to once per week or less if laboratory abnormalities stabilize or the IP has been discontinued AND the subject is asymptomatic
- Obtain PT/INR, fractionated bilirubin and any other potentially relevant laboratory evaluations of liver function or disease
- Obtain complete blood count (CBC) with differential to assess for eosinophilia
- Obtain appropriate blood sampling for pharmacokinetic analysis if this has not already been collected

- Obtain a more detailed history of:
 - Prior and/or concurrent diseases or illness
 - Exposure to environmental and/or industrial chemical agents
 - Symptoms (if applicable) including right upper quadrant pain, hypersensitivity-type reactions, fatigue, nausea, vomiting and fever
 - Prior and/or concurrent use of alcohol, recreational drugs and special diets
 - Concomitant medications (including non-prescription medicines & herbal and dietary supplements)
- Initiate full viral and autoimmune hepatitis evaluation (serologies for hepatitis A,B,C, D, E, Epstein-Barr Virus, Herpes Simplex Virus, etc); evaluate for other potential causes of DILI including but not limited to: NASH, hypoxic/ischemic hepatopathy, and biliary tract disease
- Obtain gastroenterology or hepatology consult
- Perform appropriate liver imaging or biopsy if clinically indicated; strongly consider these tests in cases of concurrent transaminase and TBL elevation as specified in [Section 6.1.3.2](#).
- Follow the subject until all laboratory abnormalities return to baseline or normal. The “close observation period” should continue for a minimum of 4 weeks after drug discontinuation.

The potential DILI event and additional information such as medical history, concomitant medications and laboratory results must be captured in corresponding eCRFs.

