6.1.3.2 Elevation of Liver Function Tests

Subjects with abnormal hepatic laboratory values (eg, alkaline phosphatase [ALP], AST, ALT, total bilirubin [TBL] or international normalized ratio [INR]) or signs/symptoms of hepatitis may meet the criteria for withholding of IP.

IP must be discontinued and the subject should be followed according to the recommendations in [Appendix B](#) (Additional Safety Assessment Information) for possible drug-induced liver injury (DILI), if ALL of the criteria below are met:

- TBL > 2x upper limit of normal (ULN) or INR > 1.5

AND

- AST or ALT > 3x ULN

AND

- no other cause for the combination of laboratory abnormalities is immediately apparent; important potential causes for abnormal AST/ALT or TBL values include, but are not limited to:
 - Obstructive gall bladder or bile duct disease
 - Viral or alcoholic hepatitis (eg, Hepatitis A/B/C/D/E, Epstein-Barr Virus, cytomegalovirus, Herpes Simplex Virus, Varicella)
 - Progression of malignancy involving the liver (note that metastatic disease to the liver, by itself, should not be used as an explanation for significant AST/ALT elevations)
 - Hypoxic or ischemic hepatopathy or congestive hepatopathy in association with significant right sided heart failure
 - Concomitant administration of other hepatotoxins, including drugs that inhibit bilirubin glucuronidation (eg, indinavir, atazanavir, irinotecan) or herbal or dietary supplements
 - Heritable disorders causing impaired glucuronidation (eg, Gilbert's Syndrome); alpha-one antitrypsin deficiency
 - Autoimmune hepatitis
 - Nonalcoholic steatohepatitis (NASH) or other "fatty liver disease"

IP should also be withheld and the subject should be evaluated for DILI if ANY of the following criteria are met:

- AST or ALT > 8x ULN at any time
- AST or ALT > 5x ULN but < 8x ULN for ≥ 2 weeks
- TBL > 3x ULN at any time
- ALP > 8x ULN at any time
- Clinical signs or symptoms that are, in the opinion of the investigator, consistent with hepatitis (such as right upper quadrant pain/tenderness, fever, nausea, vomiting, jaundice, rash or eosinophilia > 5%). If such signs or symptoms are coupled with ALT or AST elevations > 3x ULN, IP should be withheld.

If IP is withheld due to any of the conditions above, the subject should be followed according to recommendations in [Appendix B](#) for possible DILI.

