7.1.2.4 Laboratory Assessments

All on-study laboratory samples will be processed and sent to the central laboratory. Amgen or designee will be responsible for anti-AMG 145 antibody assessments and the central laboratory will ship the samples to Amgen or a specialty laboratory for assay (depending on the assessment).

The central laboratory will provide a study manual that outlines handling, labeling, and shipping procedures for all blood samples. The date and time of sample collection will be recorded in the source documents at the site.

[Table 1](#) below outlines the specific analytes for serum chemistry, hematology, urinalysis, and other testing to be conducted.

Table 1. Analyte Listing

Chemistry	Coagulation	Urinalysis	Hematology	Other Labs
Sodium	PT/INR (per Appendix B)	Specific gravity	Hemoglobin	Fasting lipids
Potassium		pH	Hematocrit	• Total cholesterol
Chloride		Blood	MCV	• HDL-C
Bicarbonate		Protein	MCH	• LDL-C
Total protein		Glucose	MCHC	• Triglycerides
Albumin		Bilirubin	RDW	• VLDL-C
Calcium		WBC	Platelets	• Non-HDL-C
Magnesium		RBC	RBC	ApoA1
Phosphorus		Epithelial cells	WBC	ApoB
Glucose		Bacteria		ApoB/ApoA1 ratio
BUN or Urea		Casts		Total Cholesterol/HDL-C ratio
Creatinine		Crystals		hsCRP
Uric acid		Microalbumin		Lp(a)
Total bilirubin				Vitamin E
Direct bilirubin				Anti-AMG 145 antibodies
CK				HbA1c
ALP				Urine Pregnancy test
LDH				HCV antibodies
AST (SGOT)				HCV viral load
ALT (SGPT)				FSH (if applicable)

High risk subjects for HCV for this protocol are those who meet any of the following conditions:

- Ever injected illegal drugs
- Received clotting factors made before 1987
- Received blood/organs before July 1992 or were exposed to blood known to be infected with HCV
- Were ever on chronic hemodialysis
- Are known to be infected with HIV
- Have a known HCV infected sexual partner

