9.2 Serious Adverse Events

9.2.1 Definition of Serious Adverse Events

A serious adverse event (SAE) is defined as an adverse event that meets at least 1 of the following serious criteria:

- fatal
- life threatening (places the subject at immediate risk of death)
- requires in-patient hospitalization or prolongation of existing hospitalization
- results in persistent or significant disability/incapacity
- congenital anomaly/birth defect
- other medically important serious event

An adverse event would meet the criterion of "requires hospitalization", if the event necessitated an admission to a health care facility (eg, overnight stay).

If an investigator considers an event to be clinically important, but it does not meet any of the serious criteria, the event could be classified as a serious adverse event under the criterion of "other medically important serious event". Examples of such events could include allergic bronchospasm, convulsions, blood dyscrasias, drug-induced liver injury (see [Appendix B](#)) for drug-induced liver injury reporting criteria, or events that necessitate an emergency room visit, outpatient surgery, or urgent intervention.

If adverse events correspond to grade 4 “life threatening” CTCAE (eg, laboratory abnormality reported as grade 4 without manifestation of life threatening status), it will be left to the investigator’s judgment to also report these abnormalities as serious adverse events. For any adverse event that applies to this situation, comprehensive documentation of the event’s severity status must be recorded in the subject’s medical record.

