8.4.4 Analyses of Laboratory Measurements

Descriptive statistics will be provided for actual values and changes from baseline in each applicable laboratory parameter at each protocol-specified scheduled visit.

Laboratory analytes are provided in the protocol Table 7. Lab shift table using the CTCAE v4.03 **or later** grading will be used for the select analytes of interest, when applicable. Shift tables will be provided for the SOC-Controlled period and the All-IP period. The results will be based on the maximum (ie. worst) shift from parent baseline to the end of the SOC-Controlled period and from the parent baseline to end of the All-IP period, respectively.

In addition, CK and liver function test (LFT) abnormalities will be assessed by the incidence during the SOC-Controlled period and during the All-IP period:

- CK > 5 x ULN
- CK > 10 x ULN
- ALT or AST > 3 x ULN
- ALT or AST > 5 x ULN
- Total bilirubin > 2 x ULN
- (ALT or AST > 3 x ULN) and (Total bilirubin > 2 x ULN or INR > 1.5)

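### Appendix B gives the INR limit for 24-hour liver-injury reporting as a multiple of ULN, while Protocol 6.1.3.2 and SAP 8.4.4 use an absolute INR above 1.5

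*Protocol*

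**What the plan says.** Protocol Section 6.1.3.2 requires investigational product (IP) to be discontinued for possible DILI when three conditions hold together: "TBL > 2x upper limit of normal (ULN) or INR > 1.5"; "AST or ALT > 3x ULN"; and no readily evident alternative explanation for the abnormalities. INR is stated there as a plain number.

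Protocol Appendix B, under DILI reporting, covers "cases of concurrent AST/ALT and TBL elevation according to the criteria specified in" Section 6.1.3.2. It then restates those criteria in parentheses, ending with "2x ULN for TBL or INR>1.5 ULN". The duty attached to them is explicit: "The event should be reported to Amgen as a serious adverse event within 24 hours of discovery or notification of the event".

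SAP Section 8.4.4 defines its combined liver abnormality as ALT or AST above 3x ULN together with "Total bilirubin > 2 x ULN or INR > 1.5". Here too INR is an absolute value.

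Two other places point to Appendix B. Protocol Section 9.2.1 refers the investigator to it "for drug-induced liver injury reporting criteria", and Table 1 in Section 7.1.2.4 lists "PT/INR (per Appendix B)" among the laboratory tests. Neither states an INR limit.

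**The concern.** The stopping rule and the expedited-reporting rule are meant to describe the same liver signal, yet as printed they use different INR limits. Whenever the ULN for INR is above 1.0, 1.5 times ULN is a higher bar than 1.5. Some subjects would then meet the stopping rule and the SAP category but not the printed reporting rule.

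The lead-in to the reporting paragraph makes this slightly worse. It mentions only transaminase and bilirubin elevation, so for a case that qualifies through INR the parenthesis is the only INR wording a reader finds in that paragraph.

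At stake is a late or missing expedited report of possible DILI in a study whose primary objective is safety. The SAP laboratory table could also count a combined liver abnormality with no matching SAE report.

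**Working it through.** The documents state no figure to reproduce. The check is a comparison of the three thresholds, followed by one line of arithmetic.

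**Thresholds side by side**

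| Place | Purpose | Transaminase | Bilirubin | INR |
|---|---|---|---|---|
| Protocol 6.1.3.2 | Discontinue IP | > 3x ULN | > 2x ULN | > 1.5 |
| Protocol Appendix B | 24-hour SAE report | 3x ULN | 2x ULN | > 1.5 ULN |
| SAP 8.4.4 | Tabulated abnormality | > 3x ULN | > 2x ULN | > 1.5 |

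In each row the bilirubin and INR conditions are alternatives, and the transaminase condition is always required. Two of the three places give an absolute INR; Appendix B alone gives a multiple.

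**Who falls between the rules.** The subject must have:

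- AST or ALT above 3x ULN;
- bilirubin not above 2x ULN, since otherwise the bilirubin condition triggers reporting anyway;
- no alternative explanation readily evident; and
- 1.5 < INR ≤ 1.5 × ULN.

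**Width of the gap.** The ULN for INR is not in the documents, so it is an assumption, shown as a range. Upper end = 1.5 × ULN; width = 1.5 × ULN − 1.5.

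| Assumed ULN | Upper end | Width |
|---|---|---|
| 1.0 | 1.5 × 1.0 = 1.50 | 0 |
| 1.1 | 1.5 × 1.1 = 1.65 | 0.15 |
| 1.2 | 1.5 × 1.2 = 1.80 | 0.30 |
| 1.3 | 1.5 × 1.3 = 1.95 | 0.45 |

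**Example.** With an assumed ULN of 1.2, take a subject with INR 1.6, bilirubin not above 2x ULN, AST or ALT above 3x ULN and no evident other cause. Because 1.6 > 1.5, Section 6.1.3.2 requires IP to stop and SAP 8.4.4 counts the case. Because 1.6 ≤ 1.80, the printed Appendix B limit is not met. The case then falls under the Appendix B provision for other hepatotoxicity, where SAE status depends on the general definition in Section 9.2.1.

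**Availability of INR.** The schedule in Appendix A has coagulation only at Day 1 and Weeks 48, 104 and 152. However, Appendix B calls for PT/INR in any subject whose AST or ALT exceeds 3x ULN, so an INR should usually exist for the subjects who matter here. The number affected cannot be derived from the documents.

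**The case against.** The best defence is that Appendix B names its own governing text. The parenthesis is shorthand for Section 6.1.3.2: it also drops the greater-than signs for transaminases and bilirubin and leaves out the third condition, so it was never a free-standing definition. The chain from Section 9.2.1 to Appendix B to Section 6.1.3.2 ends at the correct value. To go wrong, a site would have to apply 1.5 when stopping IP and then a different limit when reporting.

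The safety net is also real. Transaminases above 3x ULN alone bring close observation with repeat liver tests, PT/INR and a specialist consultation, and potential DILI must be captured in the eCRF. Section 9.2.1 gives DILI as an example of a medically important serious event, and an SAE reported by that route has the same 24-hour deadline under Section 9.2.2. SAP 8.4.4 applies its own limit directly to the laboratory data, so no planned analysis threshold moves.

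All of this stands, and it keeps the point minor. It does not remove the mismatch. The parenthesis looks like a full restatement, so a reader sent to Appendix B for the reporting criteria has little reason to look further. The Section 9.2.1 route depends on investigator judgment, whereas the Appendix B rule was written to be automatic. The Table 1 pointer carries little weight either way, since it sits in a list of analytes and sets no threshold.

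**Conclusion.** The inconsistency is real and sits in operative safety text. Appendix B should use an absolute INR above 1.5, as Section 6.1.3.2 and SAP 8.4.4 do; the stray ULN is almost certainly a drafting error.

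The practical effect is small. It is confined to subjects who meet the bilirubin/INR condition through INR alone, and to a band that is empty if the ULN is 1.0 and extends from 1.5 to at most 1.95 over the assumed ULN range of 1.0 to 1.3. A site that follows the cross-reference reports correctly. The consequence is a possible delayed or missed expedited report, or a serious/non-serious classification that differs between sites. The case itself is not lost to follow-up, and the lipid endpoints are unaffected. Severity: minor. Confidence in the textual mismatch is high; how often it would matter is unknown.

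**What to change.** In Protocol Appendix B, delete ULN after the INR limit so that it reads INR > 1.5. All three places then agree and the gap closes whatever the local ULN. The SAP needs no change.

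A useful but optional addition is to reword the Appendix B lead-in so that it names elevation of AST/ALT together with TBL or INR, making clear that INR-qualified cases are included.

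The cost is one deleted word, made at the next protocol amendment or sooner by a clarification to sites. Design, data collection and analysis are untouched.
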